## 1 BACKGROUND

Intravital microscopy (IVM) is the microscopic observation of living tissue in real time. IVM has been successfully applied to the investigation of the tumor microvasculature of human primary melanoma.[3] It has been shown that tumor vessels lack the sequential hierarchy of normal vessels such that arterioles, capillaries, and venules typically cannot be discriminated within tumor tissues.[4, 5] This disorganization of aberrant tumor vessels was demonstrated in a previous feasibility clinical trial.[2] These tumor-associated vessels were characterized by irregular diameters, aberrant branching patterns, abnormal blood flow rates, and anastomotic structures. More specifically, the human tumor-associated vessel diameters observed in real time *in vivo* were larger than those predicted either by *in vivo* mouse models or by human immunohistochemistry (IHC) on tumor specimens analyzed *ex vivo*.[3] These characteristics could have profound influence on the delivery of agents (i.e., chemotherapy or cellular immunotherapy) to the tumor microenvironment.[6]

In order to obtain this data, human intravital microscopy (HIVM) was used first in melanoma primary tumors. Intravital microscopy (IVM) has also been used to directly examine the hemodynamic properties of tumor microvessels in preclinical mouse models.[1, 7-9] These studies were primarily based on the analysis of blood vessels and leukocytes labeled *in situ* with fluorescent tracking dyes (e.g., fluorescein or ICG). Recent mouse studies in B16 murine melanoma have used IVM to demonstrate that the abnormal, tortuous vascular structure in tumors represents a bottleneck to adoptive cell transfer immunotherapy because of poor trafficking of cytotoxic effector T cells at this site.[1] Others have used different forms of IVM to observe lymphatics or metastatic disease in real time in mouse models.[10, 11] There has also been reported real time imaging of human tumor and lymphatics using different techniques such as multiphoton imaging, high resolution ultrasound, or optical coherence tomography.[12, 13] To date, there have been no studies of IVM in the setting of human peritoneal carcinomatosis.

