#### 3.2 SECONDARY OBJECTIVES - PART II (20 PATIENTS):

1. Compare the microscopic observation of the tumor-associated vessels with normal tissue (peritoneal surface) in each individual subject.
2. Correlate the microscopic observations of the tumor-associated vessels with pathologic grade of tumor implants.
3. To correlate the microscopic observation of the microvasculature with tumor-specific and overall survival.

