#### 3.3 PRIMARY AND SECONDARY ENDPOINTS:

*Primary endpoint:* A patient will be deemed a success if each of the following parameters were measured:

1. Identify tumor implant associated vessels and measure vessel diameters
2. Determine vessel density per 10x field
3. Visualize vital dyes within the tumor-associated vessels (fluorescein and green ICG)
4. Calculate the blood flow velocity of the tumor-associated vessels and tissue penetration of fluorescein and ICG as markers of vessel permeability.

*Secondary endpoints:*

1. Post-operative comparison of the microvasculature of peritoneal carcinomatosis with normal tissue (peritoneum) in each individual subject using vessel diameters, vessel density, detection of intravital dye and flow rates.
2. Post-operative correlation of the microvasculature with pathologic features of the tumor implants (i.e. tumor grade) at the time of the final pathology report (5-7 days after surgery).

3. Post-operative correlation of the microscopic observation of the tumor microvasculature tumor-specific and overall survival.

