Technical difficulties with the microscope apparatus (e.g. malfunction of the software or structural damage to any of the microscope components) or unforeseen events during the course of surgery that are unrelated to the study intervention but that result in the termination of the surgery (e.g. adverse reaction to anesthetic prior to administration of intravital dye or hemodynamic instability from a complication of the surgery) will not be considered failures of the primary objective. In these circumstances, the subject will be considered to be off-study and be replaced with a subsequent patient.

Off-line analysis of digitally recorded live video will be performed using parameters and statistical methods that have been developed in our preclinical imaging studies.[1] Lumenal cross-sectional diameter (D) of vessels and velocity (V) of dye labeled cells will be measured in off-line observations. Wall shear rate ( $\gamma$ ) will be calculated as  $8(V \div D)$ .[92] Vessel density will be determined by measuring the calculated blood vessel area as a percent of the total visual field area. If visible, the uptake of fluorescein or ICG will be measured as a diffusion rate (distance from tumor vessel over time) and as a percent of the total tumor field observed (percent of visual field expressed as surface area with dye detected). Blood flow velocity will be determined by the equation  $Q = (RBC \text{ velocity}/1.6) \times (d/2) \times \pi$ .

These data will be calculated and recorded in a spread sheet that will also be saved onto a password-protected hard drive in the Principal Investigator's laboratory. Additionally, all data will be de-identified and provided to the Biostatistician. Generated data and the raw video images will be stored for review at any time to satisfy any audit of the collected data. This saved data will readily allow the determination of a successful observation including the identification of tumor vessels, the associated vessel measurements, vessel density, and dye enhanced imaging acquisition.

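### The equation given for blood flow velocity does not produce a velocity, and the plan does not say whether the tumor-versus-normal flow rate comparison uses velocity or that equation's result

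*Combined protocol and SAP*

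**What the plan says.** Section 4.2 (Study Methods) lists what is taken from the video: "Lumenal cross-sectional diameter (D) of vessels and velocity (V) of dye labeled cells will be measured in off-line observations". Wall shear rate is then 8(V/D). A few lines later the section says "Blood flow velocity will be determined by the equation" and gives, as extracted and without its opening bracket, "RBC \text{ velocity}/1.6) \times (d/2) \times \pi", that is, Q = (RBC velocity/1.6) × (d/2) × π. No other flow equation appears. The section also says, in general terms and with a citation, that the off-line analysis follows methods from the group's earlier preclinical imaging work.

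The measure goes by different names elsewhere:

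- Section 3.3, primary endpoint item 4: "Calculate the blood flow velocity of the tumor-associated vessels and tissue penetration of fluorescein and ICG as markers of vessel permeability".
- Section 3.3, secondary endpoint 1: a within-patient comparison of tumor and normal peritoneum "using vessel diameters, vessel density, detection of intravital dye and flow rates".
- Section 9, abnormality criterion 5: a low average blood flow rate relative to a normal vessel, with one standard deviation as the margin.
- Section 9, matched analysis: a paired t test on average blood flow rate.

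Neither the protocol body nor Section 9 defines flow rate or ties it to V or to Q.

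**The concern.** A velocity is length per time and a volumetric flow is volume per time. The one equation supplied is named as the first, carries the symbol and most of the ingredients of the second, and as printed is neither. An analyst who follows it literally will record a wrong quantity for endpoint item 4.

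The larger exposure is the paired t test on average blood flow rate. It belongs to the secondary objectives, which Section 3.2 assigns to the 20 patients of Part II. Velocity, Q as printed and volumetric flow depend differently on vessel diameter, so they need not agree on whether tumor flow is lower or higher than normal. If the quantity is not fixed beforehand, it can be chosen after the results are visible. Criterion 5 uses the same undefined term, but it is one of five alternative triggers and Section 9 specifies no test of the composite.

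**Working it through.** The plan gives no effect size, standard deviation, significance level or power for this comparison, so there is no stated figure to reproduce. The check is of the equation itself.

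**Inputs.** From Section 4.2: measured diameter and velocity, and the equation for Q. Assumed, because the documents give neither: tumor/normal diameter ratio r and tumor/normal velocity ratio v.

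**Step 1: units.** Write L for length and T for time.

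- RBC velocity/1.6: L/T, a velocity.
- Q as printed: (L/T) × L = L²/T, neither a velocity nor a volumetric flow.
- Q with (d/2)²: (L/T) × L² = L³/T, a volumetric flow but not a velocity.
- Shear rate 8(V/D): (L/T)/L = 1/T, as it should be.

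For an assumed vessel with velocity 1600 µm/s and diameter 20 µm:

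- 1600/1.6 = 1000 µm/s
- as printed, 1000 × 10 × π = 31,416 µm²/s
- with the square, 1000 × 10² × π = 314,159 µm³/s

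**Step 2: tumor/normal ratios for one vessel pair.** The constants 1.6, 2 and π cancel. Velocity gives v, Q as printed gives v × r, and volumetric flow gives v × r².

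| r (assumed) | v (assumed) | velocity: v | as printed: v × r | volumetric: v × r² |
|---|---|---|---|---|
| 2 | 0.4 | 0.40 | 0.80 | 1.60 |
| 1.25 | 0.72 | 0.72 | 0.90 | 1.125 |
| 1.25 | 0.9 | 0.90 | 1.125 | 1.41 |
| 0.8 | 1.4 | 1.40 | 1.12 | 0.90 |
| 1 | any | v | v | v |

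**Step 3: when the direction differs.** A ratio below 1 means lower in tumor. Velocity and volumetric flow point opposite ways when v lies between 1/r² and 1:

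- r = 2: v from 0.25 to 1
- r = 1.25: v from 0.64 to 1
- r = 1.1: v from 0.83 to 1
- r = 0.8: v from 1 to 1.56

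In every case diameter and velocity have to shift in opposite directions.

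**Step 4: averages over several vessels.** These windows hold vessel by vessel, whereas Section 9 uses an average flow rate. Take equal velocities everywhere, tumor diameters 10 and 30, and normal diameters 20 and 20 (assumed). Mean diameter and mean velocity ratios are both 1, yet the mean volumetric ratio is (5² + 15²)/(10² + 10²) = (25 + 225)/(100 + 100) = 1.25. The candidates can therefore differ even when average diameters are equal, and the windows in Step 3 are only a guide.

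**Step 5: the factor 1.6.** Dividing both members of every pair by 1.6 scales the mean difference and its standard error equally, so the paired t statistic is unchanged. Only absolute values move (1/1.6 = 0.625).

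**The case against.** The strongest reply is that this is a typesetting slip. Q, π and (d/2) are what one would expect in a volumetric flow, and one lost superscript restores it. That stands as far as it goes: the missing square cannot be called the authors' error from this text. It does not rescue the label, because a volumetric flow is still not a velocity.

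A second reply is that flow rate in Section 9 most naturally means Q, the only flow equation given. That may be the intent, but it is an inference, since Section 4.2 calls Q a velocity. The general reference to earlier preclinical methods might settle it, but that source cannot be checked here, and the equation itself carries no citation.

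Third, velocity and volumetric flow could differ in direction without contradiction, because they are different quantities. That is true, and it is why the plan should say which one is tested.

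A reader might also infer that reversal is to be expected because tumor vessels are wider than normal. The documents do not support this. Section 1 says "These tumor-associated vessels were characterized by irregular diameters, aberrant branching patterns, abnormal blood flow rates, and anastomotic structures", which gives no direction against normal tissue. Its statement that human tumor vessels were larger compares them with mouse models and with immunohistochemistry of excised specimens.

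Finally, the 1.6 factor, and whether RBC velocity is the measured V, change no test.

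**Conclusion.** The point holds. The stated rule does not yield a velocity on either reading of the exponent, and as printed it yields no valid flow measure. By inference the problem extends to one secondary paired t test and one of five abnormality triggers, because Section 9 does not identify the quantity it uses.

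The choice can change the direction of the tumor-versus-normal comparison. This is a possibility and not a prediction: it rests on assumed single-vessel ratios, requires diameter and velocity to move in opposite directions within the windows shown, and carries over only approximately to averages.

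A reader might infer that the seven-of-ten feasibility decision is at risk, since item 4 is part of it. It is not: that rule counts patients in whom the quantities could be obtained and does not use their values. The matter should be corrected before analysis, and it does not threaten the primary conclusion.

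**What to change.** 1. Check the exponent on (d/2) against the source document. If the square is absent, correct the equation to (RBC velocity/1.6) × π × (d/2)² and call the result volumetric flow rate, in volume/time. If the square is present, correct only the label.
2. In either case, report velocity separately, in length/time, for endpoint item 4.
3. Before analysis, state which of the two quantities is the flow rate in secondary endpoint 1, abnormality criterion 5 and the paired t test, and use one term for each throughout.
4. Recalculate any values already derived.
5. As a minor clarification, say what 1.6 represents and whether RBC velocity and d are the measured V and D.

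The cost is a few lines of text and a spreadsheet recalculation. Diameter and velocity are measured off-line, and Section 4.2 says "Generated data and the raw video images will be stored for review at any time", so no new patient data are needed.

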## **TARGET ACCRUAL AND STUDY DURATION**

A maximum of 30 subjects [Part I (10 patients) and Part II (20 patients)] will be enrolled. The number of subjects required is a function of the expected feasibility. Accrual is expected to take up to 2.5 years.

## **5 SUBJECT SELECTION**

Patients who are scheduled to undergo CRS-HIPEC in the operating room who can provide informed consent, have a good performance status (ECOG  $\leq 2$ ), and have no known allergy or prior reaction to fluorescein, ICG or iodine, are eligible.

### **5.1 INCLUSION CRITERIA**

1. Age  $\geq 18$  years of age.
2. Have an ECOG Performance Status of  $\leq 2$ . Refer to Appendix C.
3. Have measurable disease in the peritoneum by direct visualization (visible lesion typically  $> 0.5$  cm in maximal diameter).
4. Carcinomatosis that meets indications for CRS-HIPEC.
5. Subject must understand the investigational nature of this study and sign an Independent Ethics Committee/Institutional Review Board approved written informed consent form prior to receiving any study related procedure.
6. A negative skin-prick test to fluorescein.

### **5.2 EXCLUSION CRITERIA**

1. Uncontrolled intercurrent illness including, but not limited to, ongoing or active infection, symptomatic congestive heart failure, unstable angina pectoris, cardiac arrhythmia, or

psychiatric illness/social situations.
2. Renal dysfunction as defined as a GFR < 45.
3. Liver dysfunction as defined by Child-Pugh score > 5, or LFT's 1.5x above normal range.
4. Any known allergy or prior reaction to fluorescein or ICG or a positive skin prick test to fluorescein.
5. Pregnant or nursing female subjects, determined preoperatively with a urine pregnancy test.
6. Unwilling or unable to follow protocol requirements.
7. Any condition which in the Investigators' opinion deems the patient unsuitable (e.g., abnormal EKG).
8. Any condition that excludes CRS-HIPEC as the standard of care for the patient.

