			7. Any condition which in the Investigators' opinion deems the patient unsuitable (e.g., abnormal EKG).	
			8. Any condition that excludes CRS-HIPEC as the standard of care for the patient.	

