ICG is an iodide-containing, water soluble tricarbocyanine dye that fluoresces when exposed to infrared light (800 nm).[57] Compared to Fluorescein, the molecular weight of ICG is over double at 774.98 g/mol (Fluorescein molecular weight is 332.31 g/mol). The package insert and the Material Safety Data Sheet are shown in the Appendix B.

Following IV injection, ICG is rapidly bound to plasma proteins of which albumin is the main carrier (95%).[55, 58] The drug undergoes no significant extrahepatic or enterohepatic circulation; it is taken up mainly by hepatic parenchymal cells and excreted into bile.[55, 59] It has a plasma half-life of approximately 3-4 minutes.[55, 58] Due to its high binding to albumin and significantly greater molecular weight than Fluorescein, ICG is expected to persist within the tissues for a longer period of time resulting from a slower washout. This characteristic would have several advantages to the study of HIVM in tumor associated vessels, including increased imaging times, more extensive characterization of blood vessel architecture, and more accurate calculation of blood flow velocities.

The ICG will be provided by the study. It will be ordered and sent to the operating room during surgery at the time of the planned HIVM observation. The dose to be administered will be calculated prior to the surgery based on the patient's most accurate and current weight. It will be

injected through the IV by a physician member of the surgical or anesthesia team. Surgeons and anesthesiologists have experience with the IV administration of ICG during other procedures, such as injection during plastic surgery reconstructive procedures to assess tissue viability.

Similar to Fluorescein, ICG has a rare incidence of anaphylactic reaction (0.05 – 0.15%). It does contain an iodide component, which accounts for the allergy potential of ICG. Therefore, patients with a known allergy to iodine or contrast dye will be excluded from the study. Patients who have received iodine based contrast computerized tomography (CT) scans with IV iodine contrast dyes would be unlikely to have an iodine allergy, particularly if multiple scans have been performed. During the staging of patients with peritoneal carcinomatosis, routine use of imaging is routinely recommended to investigate the degree of metastasis. Thus, it is extremely unlikely that a patient who has received IV iodine contrast dye during a CT scan will have an allergic reaction to ICG.

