#### **1.4.2 CLINICAL STUDIES WITH ICG**

Similar to Fluorescein, ICG is not expected to have a direct intervention on tumor biology. ICG has been used during the course of surgery and other procedures for widespread indications and is FDA approved. In general, it is well tolerated, non-toxic, and has no long term side effects.

Clinically, ICG is most commonly used in the assessment of liver function,[63-65] ophthalmic angiography,[66-68] and the analysis of cardiac function with increasingly novel applications in cardiac studies.[69, 70] It is typically administered by a member of the anesthesia team during cases or procedures in the operating suite under general anesthesia. In addition to these applications, ICG has been used in a variety of other studies in a safe manner. ICG has been used to map sentinel lymph nodes (SLN) in several malignancies,[71] including melanoma,[56, 72, 73] breast,[74-76] and colon cancer.[77] These studies have not reported any major adverse reactions or toxicities resulting from exposure to ICG. While the doses of ICG used in these studies varies, the recommended dose per the manufacturer is calculated on the basis of 0.5 mg/kg of body weight.[55]

Other applications of ICG have been studied in the field of plastics surgery. ICG has been given in patients to determine the perfusion and viability of perforator flaps.[78, 79] Similar to the studies in malignancy and SLN, the fluorescent properties of ICG have been utilized and shown to be effective in other studies. ICG has also been used to identify and target esophageal varices.[80] Further, during neurovascular operations, ICG has been readily administered by

anesthesiologists during intraoperative videography of aneurysm clippings and carotid bypass procedures.[81, 82]

As discussed in the previous section, the use of ICG is contraindicated in patients with a history of allergic hypersensitivity to iodine. There have been rare but reported cases of anaphylaxis and death due to allergic reactions during procedures using ICG.[25, 83, 84] Therefore, patients with a history iodine allergy will be excluded from our clinical trial. Other adverse reactions have been reported with the use of ICG in patients with allergic reactions.[85]

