## 4 METHODOLOGY

### 4.1 Study Design

This is an open-label, non-randomized, single center, study of IVM observation in conjunction with fluorescein and ICG in subjects with peritoneal carcinomatosis undergoing CRS-HIPEC. The first part is a Pilot study of feasibility.

Subjects will be treated on an inpatient basis. All subjects will meet the inclusion and exclusion criteria summarized in **Section 5.1** and **Section 5.2** prior to participation in this study. Standard evaluation by the Preoperative Anesthesia clinic may include additional testing such as EKG, chest x-ray, and/or pulmonary function tests, but this is performed based upon their established guidelines. If any of these tests preclude a wide excision in the operating room, then the patient is excluded from this study.

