## **6 STUDY PROCEDURES**

### **6.1 BASELINE EVALUATIONS**

Standard presurgical assessment with labs and studies as determined by the preoperative Anesthesia clinic based upon their established guidelines.

The following will be performed within 1 week prior to the planned microscopic observation:

- Informed consent: Must be completed prior to receiving any study-related procedures.
- Medical history
- Physical examination, including vital signs (i.e., temperature, heart rate, respiratory rate, blood pressure, body weight, and height).
- If determined to be eligible for the study and after giving informed consent, a skin-prick test to determine sensitivity and risk of anaphylaxis to fluorescein and a patch test for ICG will be

performed by the Principal Investigator. For testing allergic response to fluorescein, a sterile Duotip® lancet (Lincoln Medical, USA) is used in 3 separate areas of skin on the forearm. The skin-pricks will include 4 microliters of 10% fluorescein, histamine chloride (10 mg/ml) [positive control], and 50% saline solution [negative control] administered in areas of skin prepped with an alcohol pad. After 30 minutes, the appearance of a wheal greater than 3 mm in diameter is considered a positive test result in the context of the appropriate positive and negative control. If a positive test is noted, the patient will no longer be eligible for this study. For comfort and relief of any skin irritation/pruritis, the patient will be offered an anti-histamine (fexofenadine [Allegra®] 30 mg po x 1) following the skin-prick test if necessary. The patient will also be screened for a history of allergic reaction to iodine or iodinated contrast dyes.

- If indicated by anesthesia pre-op assessment (standard operating procedure for pre-op clinic)  
- Hematology [i.e., CBC (with or without differential, auto or manual), ANC, and platelets].
- A complete metabolic panel (CMP): chloride, Co2, potassium, sodium, BUN, glucose, calcium, creatinine, total protein, albumin, total bilirubin, alkaline phosphatase, AST, ALT, A/G ratio, BUN/creatinine ratio, osmol (Calc), anion gap).

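### The numbered exclusion criteria and the enrolment checklist omit the iodine and contrast-dye allergy that other sections of the protocol say excludes a patient

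*Combined protocol and SAP*

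**What the plan says.** Three numbered lists govern entry: the synopsis, the eligibility checklist, and Sections 5.1 and 5.2. In all three, exclusion 4 reads "Any known allergy or prior reaction to fluorescein or ICG or a positive skin prick test to fluorescein". Section 4.1 refers the reader to the last pair: "All subjects will meet the inclusion and exclusion criteria summarized in" Sections 5.1 and 5.2. The checklist allows enrolment only if every exclusion line is answered no or not applicable.

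The narrative sections go further:

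- Section 1.4: "patients with a known allergy to iodine or contrast dye will be excluded from the study".
- Section 1.4.2: "the use of ICG is contraindicated in patients with a history of allergic hypersensitivity to iodine". After noting reported anaphylaxis and deaths, it adds that "patients with a history iodine allergy will be excluded from our clinical trial".
- Section 5 lead-in: patients who, among other conditions, "have no known allergy or prior reaction to fluorescein, ICG or iodine, are eligible".
- Section 6.1: "The patient will also be screened for a history of allergic reaction to iodine or iodinated contrast dyes".

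The ICG product sheet in Appendix B is milder and advises only caution in patients with a history of iodide allergy.

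**The concern.** A safety rule that the protocol states as mandatory is missing from the documents used to apply it. Section 4.2 gives 5 mg of ICG intravenously during the observation, for imaging and not for treatment. The sponsor chose a stricter position on iodine allergy than the product sheet, and the reason it gives is severe allergic reaction. If the person completing the checklist relies on the numbered lines, nothing on the form tells them to exclude a patient in whom the protocol calls the dye contraindicated. What is at stake is patient safety and consistent application of the entry rule. No statistical result depends on it.

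**Working it through.** There is no planned figure to reproduce. The check is a comparison of every statement on dye allergy.

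| Place | Iodine allergy excluded? | Contrast-dye allergy excluded? |
|---|---|---|
| Synopsis, exclusion 4 | Not named | Not named |
| Checklist, exclusion 4 | Not named | Not named |
| Section 5.2, exclusion 4 | Not named | Not named |
| Section 1.4 | Yes | Yes |
| Section 1.4.2 | Yes, and ICG called contraindicated | Not named |
| Section 5 lead-in | Yes | Not named |
| Section 6.1 | History taken, no consequence stated | History taken, no consequence stated |

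Each list has 6 inclusion and 8 exclusion criteria, so 14 lines. None of the 3 × 14 = 42 lines names iodine or contrast. Most of those lines, such as age or consent, would never do so. The informative count is 0 of 3 numbered lists against 3 of 3 narrative sections (1.4, 1.4.2 and 5).

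**Test case 1: iodine allergy, no previous ICG, negative fluorescein prick test, otherwise fit.** Every inclusion line is met. On exclusion 4 the truthful answer is no, because there is no known allergy or reaction to fluorescein or ICG and the prick test is negative. The only remaining line that could stop entry is exclusion 7, "Any condition which in the Investigators' opinion deems the patient unsuitable (e.g., abnormal EKG"). It rests on the investigator's opinion and does not mention allergy. The Section 5 lead-in does bar this patient, but it appears in neither the checklist nor the synopsis.

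**Test case 2: the same patient, with the allergy recorded as being to contrast dye.** The lists behave as before. The Section 5 lead-in does not name contrast dye either, so the only explicit bar is in the drug background of Section 1.4.

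**Does the omission look deliberate?** Other dye-related exclusions in the background did reach the numbered lists:

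- Fluorescein sensitivity (Section 1.2) became exclusion 4.
- Pregnancy and nursing (Sections 1.2.2 and 1.4.2) became exclusion 5.
- Renal and hepatic disease, which Section 1.4.2 treats only as a possible ground for exclusion, became the firm exclusions 2 and 3.

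Iodine allergy, stated as a definite exclusion, did not carry over. That pattern suggests an oversight.

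**Scale.** Section 1.4 gives ICG anaphylaxis as 0.05% to 0.15%; Section 1.4.2 gives severe reactions as 0.05%. With the maximum of 30 subjects:

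- 30 × 0.0005 = 0.015 events
- 30 × 0.0015 = 0.045 events

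These are background expectations for ICG recipients in general, not the excess caused by the omission. That excess depends on how many allergic patients would be enrolled and on their reaction rate, and the documents give neither. The upper figure is also uncertain, because Section 1.4.2 gives 0.15% as the rate of mild reactions.

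**The case against.** The strongest reply is that the rule is already in the eligibility section. The Section 5 lead-in stands directly above 5.1 and 5.2 and names iodine, and Section 4.1 describes those two sections only as a summary. Exclusion 4 is silent on iodine; it does not permit such a patient to enter. The history must be taken under Section 6.1, Sections 1.4, 1.4.2 and 5 supply the consequence, and exclusion 7 gives the checklist a line on which to record it. For harm to follow, an investigator would have to elicit the allergy, overlook three statements and decline to use exclusion 7. Section 1.4 also argues that patients who have tolerated contrast CT are unlikely to be iodine-allergic, so few may be affected.

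Much of this stands. The protocol as a whole does not intend to enrol these patients, and the practical risk is low. The contrast-dye gap is partly one of wording, since Section 1.4 discusses contrast as iodine-based. But the safeguards do not close the gap. The lead-in is absent from the form that controls enrolment. Section 6.1 attaches loss of eligibility to a positive fluorescein test but no consequence to a positive iodine history. Exclusion 7 is discretionary where Sections 1.4 and 1.4.2 are mandatory.

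**Conclusion.** The concern holds. It is an internal inconsistency in a safety rule: the numbered criteria taken alone admit a patient for whom the protocol calls ICG contraindicated. The conclusion is limited to the lists and the checklist; it does not say that the protocol read in full allows entry. Its practical force assumes that staff decide eligibility from the checklist and Sections 5.1 and 5.2, as the checklist rule and Section 4.1 indicate. Expected harm is small on the protocol's general rates but cannot be estimated for iodine-allergic patients. The correction should be made because it is simple and concerns a reaction that can be fatal.

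A lesser point: Section 6.1 also requires an ICG patch test, with no stated effect on eligibility and no row in the study calendar. A positive result could reasonably be read as a known ICG allergy under exclusion 4, but the text does not say so.

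**What to change.** - In exclusion 4 of the synopsis, the checklist and Section 5.2, add *iodine or iodinated contrast dye* to the named allergens, after ICG.
- Add *iodinated contrast dye* to the Section 5 lead-in, and align Section 1.4.2, so that both match Section 1.4.
- For the ICG patch test, either make a positive result an explicit part of exclusion 4 and add a calendar row, or remove the test from Section 6.1.

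The cost is a wording amendment to one criterion in three places and to the narrative text, plus one calendar row if the patch test is kept. Section 6.1 already requires the iodine and contrast history, so there is no new procedure or visit and no change to the sample size or analysis.
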